This will be a mixed methods study in an exploratory sequential design structure involving qualitative analysis via focus groups comprised of postoperative transgender women (Stage 1), followed by the distribution and testing of a questionnaire packet to male-to-female patients planning to undergo GCS at academic transgender care centers in the United States (Stage 2). The intent of the Stage 1 focus group questions will be to clarify the presentation and severity of urogynecologic symptoms in this patient group. Moderators will also ask the participants about the type and timing of their gender confirmation surgery, additional procedures, use of hormonal therapies, and neovaginal care. Please review attached Moderator Guide for the concepts to be addressed. The themes and categories generated from the focus groups will be used to create a unique screening questionnaire for this patient population that will be tested for reliability and validity in the Stage 2 component. We estimate that about 3 to 4 focus groups will be required to reach data saturation; however, additional groups may be necessary.

Stage 2 will be conducted in coordination with participating academic medical centers with affiliated gender surgeons or internal transgender care centers with surgical providers. After patient recruitment, postoperative questionnaires will be distributed which will be comprised of the Pelvic Floor Distress Inventory-20 (PFDI-20), Pelvic Floor Impact Questionnaire-7 (PFIQ-7), WHO Quality of Life BREF (WHOQOL-BREF), and the new questionnaire created from the Stage 1. We estimate about 10 minutes will be required to complete the entire questionnaire packet. A test-retest reliability challenge will be performed two weeks later with the new questionnaire only. Patient data and questionnaire answers will be entered into a universal RedCap database. All data will be analyzed at Weill Cornell Medicine. Operative information for Stage 2 participants as well as postoperative exams and treatments will be reviewed at the time of data collection and entered for analysis.

Patient recruitment for Stage 1 will be facilitated by provider referrals through transgender clinics and LGBTQ centers as well as flyer distribution to local support groups and networks (Appendix 1). A website URL (Appendix 2) will be included on the flyer for additional participation information for both Stage 1 and Stage 2.

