During the focus group sessions, patients will be consented and reminded of confidentiality rules. In the advent that any disclosed information requires

immediate medical or supportive care, the participant will be placed in direct contact with their primary provider for further assistance. This will be explicitly written in the consent form and verbally announced prior to the start of the focus group. Focus group participants will be provided with a light meal and round trip Metrocard® for travel reimbursement.

There will be a separate informed written consent for Stage 2 participants. These will need to be reviewed and authorized by each participating institution prior to distribution.

Participants:

Male-to-female transgender patients who have either undergone or plan to undergo gender confirmative genital surgery.

Stage 1: In-person focus groups comprised of MTF postoperative patients who participate in support groups in various New York City LGBTQ centers. Participants will be selected using homogeneous sampling methods. We will also reach out to online support communities to set up virtual focus groups or phone interviews if feasible. We plan to embed snowballing sampling to permit recommended individuals to participate.

Stage 2: Patients scheduled to undergo gender confirmative genital surgery or recently completed surgery within academic transgender medicine centers in the United States. They will be recruited on a rolling basis.

Sample size/power:

- Stage 1: Three to four in-person/online focus groups, comprising 10-12 participants with possible one-on-one phone interviews until data saturation reached
- Stage 2: Estimated 100-150 patients (approx 10 patients per question)

Inclusion criteria:

- Stage 1 -- Male-to-female transgender women who are at least 4 weeks postoperative following genital surgery for gender confirmation
- Stage 2 -- Male-to-female transgender women who are scheduled to undergo surgery or are within 4 weeks postoperative
- Both stages -- Minimum age 18 years old
- Both stages -- English fluency
- Both stages -- Reliable contact information and/or permanent residence

Exclusion criteria:

- Preexisting pelvic pathology, including abnormal anatomy or baseline voiding dysfunction
- Urinary or intestinal problems prior to surgery lasting greater than 6 weeks

Primary outcomes:

- Stage 1: Characterization of genital, urologic, bowel, and sexual symptoms following male-to-female gender confirmation surgery

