- Stage 2: Validity and reliability testing of new questionnaire

Secondary outcomes:

- Frequency and severity of symptoms
- Relationship between surgical technique and symptoms
- Effect of hormonal therapy usage and symptoms
- Length of time since surgery and development of symptoms

Confounding factors:

Patient age, race/ethnicity, weight, procedure technique, presence of non-iatrogenic causes of symptoms, co-morbidity, mobility restrictions, medication interactions, diet, infection, type and duration of hormonal therapy, prostate size, sexual activity

Research setting:

Focus groups will take place at the Lesbian, Gay, Bisexual and Transgender Community Center on [name].

Stage 2 will be conducted at various academic centers within the United States.

Committed programs include Boston Medical Center and Weill Cornell Medicine.

Study team members will reach out to additional programs at national conferences and through established networks.

All data will be collected and analyzed within Weill Cornell Medicine

Study instruments:

ATLAS.ti qualitative data analysis software (Berlin, Germany)

PFDI-20 (Pelvic Floor Distress Inventory-20)

PFIQ-7 (Pelvic Floor Impact Questionnaire-7)

WHOQOL-BREF (permission for use granted)

Data collection parameters:

DEMOGRAPHICS/ PRE-TREATMENT DETAILS

- Age
- Race/ethnicity
- Height
- Weight
- BMI (body mass index)
- Smoking status
- Sexual activity
- Medications
- Date of surgery
- Type and extent of hormonal therapy usage
- Additional genital surgical procedures

- History of preoperative urologic complaints
- History of prostatic hypertrophy or prostate cancer

POST-TREATMENT DETAILS

- Operative technique
- Complications
- Postoperative care
- Resumption of hormonal therapy
- Urinary tract infections
- Sexual activity
- Medications

Qualitative data analysis:

- Stage 1: transcript coding with thematic analysis
- Stage 2: Continuous variables will be calculated using student's t- test
 - Categorical data and outcomes will be calculated using chi-square analysis
 - Multiple regression analysis will be performed to assess for a correlation between symptomatology and operative technique, hormonal therapy, or demographics
 - The new questionnaire reliability will be challenged with internal consistency testing and 2-week test-retest
 - Construct validity will be challenged with face validity and convergent validity using the other questionnaires

Ethical issues:

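### Time since surgery is a secondary aim and outcome, yet the Stage 2 packet has no stated postoperative time and the planned regression and confounder list do not name it.

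*Combined protocol and SAP*

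**What the plan says.** The combined protocol and SAP covers this point in several places.

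- **Enrolment (Inclusion criteria; Participants).** Stage 2 takes "Male-to-female transgender women who are scheduled to undergo surgery or are within 4 weeks postoperative". Participants adds: "They will be recruited on a rolling basis".
- **Packet timing (Research design).** "After patient recruitment, postoperative questionnaires will be distributed". No week, month or window after surgery is given. The one interval stated is for the repeat: "A test-retest reliability challenge will be performed two weeks later with the new questionnaire only". That interval runs from the packet, not from surgery.
- **Aims and outcomes.** Secondary aims include how symptoms change with time after surgery. Secondary outcomes include time since surgery in relation to symptom development. Neither list assigns the item to a stage.
- **Analysis (Qualitative data analysis, Stage 2).** "Multiple regression analysis will be performed to assess for a correlation between symptomatology and operative technique, hormonal therapy, or demographics". The t-test and chi-square lines beside it are generic and assign no method to the time outcome.
- **Confounding factors.** The list is long and includes diet and prostate size. The only duration in it is that of hormonal therapy.
- **Data collection parameters.** The surgery date is collected, and resumption of hormones is recorded as a post-treatment item. A packet completion date is not listed.
- **Stage 1 (Research design).** "Moderators will also ask the participants about the type and timing of their gender confirmation surgery", and the transcripts receive thematic analysis.

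**The concern.** The 4-week limit governs enrolment, not completion. A woman enrolled before surgery could answer at any later time, while one enrolled in her third postoperative week could answer that day. With several centres and no common schedule, the interval from surgery to packet can vary widely between women.

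Two things are at stake. First, a variable that the sponsor has made a secondary outcome has no quantitative analysis in Stage 2. Second, the associations of symptoms with technique and with hormone use are reported without adjustment for it. If symptoms change after surgery, and packet timing differs by technique (for example between centres) or by hormone status, part of a reported association would be an effect of timing. The hormone case is plausible because hormones may be resumed after surgery, so hormone status at the packet may itself depend on elapsed time.

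Timing also defines the state in which the questionnaire is validated. If women who have already had surgery answer near enrolment, late-onset symptoms would be seen less often in the validation data. That would not hold for every domain: Background/significance places voiding dysfunction, abnormal stream, incontinence and overactive bladder in both the immediate and the long-term period.

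**Working it through.** **Step 1: text check.** Time since surgery appears in Secondary aims and Secondary outcomes. It does not appear among the regression terms or in Confounding factors. The packet is placed after recruitment and after surgery, with no further limit. The textual gap is confirmed.

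**Step 2: inputs.** The only planned figure is the Stage 2 size under Sample size/power: 100-150 women, at about 10 per question. This implies 100/10 = 10 to 150/10 = 15 questions. The number of questions is not stated, so the figure can be inverted but not reproduced. Alpha, power and correlations are not given. Everything below assumes a two-sided 5% test and the correlations shown.

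**Step 3: leaving time out.** Let the true association between exposure x (technique or hormone status) and symptom score y, given time, be zero. Then r(x,y) = r(time,x) × r(time,y), and the false-positive rate is P(|Z + atanh(r) × √(N−3)| > 1.96).

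| r(time,x) and r(time,y), each | r(x,y) | N=100 | N=150 |
|---|---|---|---|
| 0 | 0 | 5.0% | 5.0% |
| 0.2 | 0.04 | 6.8% | 7.7% |
| 0.3 | 0.09 | 14.4% | 19.4% |

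For the last row, atanh(0.09) = 0.0902. Multiplying by √97 = 9.85 gives a shift of 0.89, and by √147 = 12.12 a shift of 1.09. A simulation of 20,000 studies with both correlations at 0.3 gave 14.8% and 20.0% unadjusted, and 4.8% and 4.9% with time in the model.

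**Step 4: cost of adding time.** Variance inflation is 1/(1 − r²), with r the correlation between time and the exposure.

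- r = 0.3: 1/(1 − 0.09) = 1.10; standard error × √1.10 = 1.05.
- r = 0.6: 1/(1 − 0.36) = 1.56; standard error × √1.56 = 1.25.

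These figures ignore any gain in precision from time explaining variation in symptoms.

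**Step 5: what the time term could detect.** At an assumed 80% power, the smallest detectable correlation is tanh(2.80/√(N−3)): 0.28 at N=100 and 0.23 at N=150, if all packets are complete.

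**The case against.** The strongest reply is that the plan is less bare than it looks, and that the bias is hypothetical.

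- **Stage 1 and the chart review.** A reader might infer that the temporal outcome has no analysis at all, or that Stage 2 can only compare different women. Neither is supported. Stage 1 women are at least 4 weeks postoperative with no upper limit, are asked about timing, and have their transcripts analysed thematically. In Stage 2, postoperative exams and treatments are reviewed, and complications and urinary infections are recorded, so dated chart events may show onset for some problems. What stands is narrower: no named quantitative Stage 2 analysis.
- **Demographics.** The surgery date sits in the data block headed demographics and pre-treatment details, so the regression's demographics term might be read to cover it. This is strained. A date is not an interval, and hormonal therapy, in the same block, is named separately.
- **Completion date.** Its absence from the list is weak evidence that it will not be kept. The list omits the questionnaire answers too, and a two-week retest cannot be scheduled without the packet date. This part is a request to confirm.
- **Size.** A reader might infer that the technique or hormone results will be biased. Nothing in the documents shows that packet timing differs by technique, centre or hormone status. The 14-19% rates need both assumed correlations at 0.3; at 0.2 the rates are 7-8%. The Background remark on poor follow-up explains why prolapse may be underestimated and says nothing about packet return here.
- **Population wording.** Research design describes the Stage 2 group as "male-to-female patients planning to undergo GCS at academic transgender care centers", while Participants has "Patients scheduled to undergo gender confirmative genital surgery or recently completed surgery within academic transgender medicine centers in the United States". Inclusion criteria agrees with Participants, so this difference is editorial.

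**Conclusion.** The point holds in limited form. It is certain from the text that the packet has no stated time after surgery and that time since surgery, a secondary aim and outcome, is missing from the Stage 2 regression terms and the confounder list. As written, the technique and hormone associations are unadjusted for packet timing.

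The size of any resulting bias cannot be known from the documents. Under the assumed correlations, the false-positive rate runs from 5% (none) through about 7-8% (0.2 and 0.2) to 14-19% (0.3 and 0.3). The associations at risk are secondary. No effect on the primary reliability or validity outcome has been quantified; for that outcome, the consequence is only that the validation claim should be limited to the times observed. The unstated packet schedule alone would be a missing detail. What makes the change worthwhile is that one inexpensive model term improves on the regression as planned.

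**What to change.** 1. In the Stage 2 regression, under Qualitative data analysis, and in Confounding factors, add time since surgery at packet completion: completion date minus the surgery date already collected.
2. Confirm that the completion date is kept in the database.
3. Under Research design, state when the packet is given relative to surgery. The window is the sponsor's choice, but it must be compatible with enrolment up to 4 weeks after surgery, since late enrolees cannot supply earlier data.
4. Report the questionnaire-based Stage 2 temporal result as a cross-sectional association within the times observed, and limit the validation claim to those times.
5. As an editorial matter, align the Research design description of the Stage 2 group with Participants.

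The cost is protocol wording, one date to confirm, one derived variable and one regression term, with no added visits. The downsides are a wider standard error (about 5% if time correlates 0.3 with the exposure, about 25% at 0.6, both assumed) and a narrower temporal claim.

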Other unique aspects of MTF patients with urologic complaints include the high dose hormonal treatments and unique neovaginal flora. The male urethra and bladder contains both alpha and beta estrogen receptors (15). Given the continuous systemic exogenous estrogen exposure, one can theorize that these receptors become activated promoting a cascade of change. This, in conjunction with an altered microbiome due to exposure to different flora after surgery, can lead to an alteration in the histology and physiology of the bladder and urethra. Anatomically, the creation of a neovagina in a previously non-occupied space below the urethra and bladder can trigger bladder irritation by mass effect, theoretically leading to the overactive bladder symptoms and voiding changes reported by some. Depending on the tissue source, the unique flora of the neovagina can seed the lower urinary tract structures, thus potentiating a reactive, potentially irritative, process.

Additionally, it has been estimated that about 8% of patients will have symptomatic neovaginal prolapse, and many will require corrective surgery (13). This is likely an underestimation as the follow-up rates for patients tends to be very low, and the lack of adequate support mechanisms for the neovagina preclude it to descend more easily than a natural vagina.

We suggest that further clarification regarding MTF postoperative urologic and pelvic floor complaints can be achieved via a mixed methods approach. By using focus group interviews to create specific evaluative questions for this unique population, we can then prospectively assess patients undergoing surgery and be more proactive in addressing their needs. A unique patient-reported outcome (PRO) questionnaire will additionally allow this patient group to feel supported and involved in their own care. In all, this will enhance the quality of our care, patient satisfaction, and success of their gender confirmatory process.

Hypotheses:

Stage 1 Unit of Analysis: To understand the urologic and pelvic floor symptoms transgender women experience following genital surgery

Stage 2 Null Hypothesis: Male-to-female gender confirmation surgery has no impact on urologic and pelvic floor symptoms including overactive bladder symptoms, incontinence, voiding dysfunction, sexual dysfunction, and prolapse.

Methodology:

Research design:

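### Stage 2 has no record of sexual complaints before surgery, so pre-existing sexual problems cannot be separated from new ones and can bias the technique comparison

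*Combined protocol and SAP*

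**What the plan says.** Under Hypotheses, the Stage 2 null hypothesis is that surgery has no impact on urologic and pelvic floor symptoms, "including overactive bladder symptoms, incontinence, voiding dysfunction, sexual dysfunction, and prolapse". Secondary outcomes include how often and how severely symptoms occur, and their relation to technique, hormonal therapy and time since surgery.

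Research design puts measurement after the operation: "After patient recruitment, postoperative questionnaires will be distributed". No preoperative administration is described. Under Inclusion criteria, Stage 2 takes women scheduled for surgery as well as women up to 4 weeks after it.

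Two exclusions deal with the state before surgery: "Preexisting pelvic pathology, including abnormal anatomy or baseline voiding dysfunction" and "Urinary or intestinal problems prior to surgery lasting greater than 6 weeks". Neither names sexual dysfunction.

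Under Data collection parameters, the pre-treatment list has "History of preoperative urologic complaints" and "History of prostatic hypertrophy or prostate cancer". It also has an item for sexual activity. It has none for earlier sexual or bowel complaints.

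The planned model is described in one sentence: "Multiple regression analysis will be performed to assess for a correlation between symptomatology and operative technique, hormonal therapy, or demographics". It names no term for symptoms before surgery.

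**The concern.** The plan protects its symptom domains unequally. Urinary symptoms are covered by an exclusion and by a history item, and bowel symptoms by an exclusion. Sexual function has neither, although it is the domain in which a woman's state before surgery is otherwise unknown.

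Two consequences follow. First, a sexual problem that was present before surgery and continues will be reported on the postoperative questionnaire and counted like a new one. Second, if prior problems are more common among women who receive one technique than another, the regression will credit that difference to technique. Women also enter with differing hormonal therapy, so the hormone association is open to a similar difficulty. Without a record of the earlier state, the analyst can neither see an imbalance nor adjust for it.

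**Working it through.** **Coverage by domain, from the documents**

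| Domain | Named in Stage 2 null hypothesis | Excluded if present before surgery | Prior history recorded |
|---|---|---|---|
| Urinary | Yes | Yes (voiding dysfunction; problems over 6 weeks) | Yes |
| Bowel | No | Yes (intestinal problems over 6 weeks) | No |
| Sexual | Yes | Not named | No |

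The sexual activity item does not fill the gap. An inactive woman may have no dysfunction, and an active woman may have it. The Confounding factors list mentions symptom causes not due to treatment, and co-morbidity, but no data item supplies either for sexual function.

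**Size: an illustration, because the documents give no rates**

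The only Stage 2 figure is the sample of 100-150, a rule of about 10 patients per question (implying 10 to 15 questions). It does not bear on this point except to set group sizes.

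Assumptions: prior problems have prevalence b and all persist; new-onset risk among the rest is s = 20% in every group; there are two equal technique groups of 50 or 75.

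*Step 1, frequency.* Observed prevalence is p = b + (1 − b)s, and the share of counted cases that predate surgery is b/p.

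- b = 10%: p = 0.10 + 0.90 × 0.20 = 28%; share 0.10/0.28 = 36%
- b = 20%: p = 0.20 + 0.80 × 0.20 = 36%; share 0.20/0.36 = 56%
- b = 30%: p = 0.30 + 0.70 × 0.20 = 44%; share 0.30/0.44 = 68%

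This inflation over the 20% new-onset risk needs no difference between groups.

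*Step 2, technique comparison.* With equal b in both groups, the false difference is zero. With unequal b, the chance that a two-sided 5% test of two proportions (n per group, mean proportion p̄) declares a difference is approximately

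Φ{ [ |p2 − p1| − 1.96√(2p̄(1 − p̄)/n) ] / √[(p1(1 − p1) + p2(1 − p2))/n] }.

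| Prior prevalence | Observed | False difference | n = 50 | n = 75 |
|---|---|---|---|---|
| 10% vs 20% | 28% vs 36% | 8 points | 0.13 | 0.18 |
| 10% vs 30% | 28% vs 44% | 16 points | 0.38 | 0.53 |

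These compare with 0.05 when there is no imbalance.

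*Step 3, on a score.* If scores before and after surgery correlate at ρ and the groups differ by 0.5 SD beforehand (both assumed), the bias is ρ × 0.5. That is 0.3 × 0.5 = 0.15 SD to 0.6 × 0.5 = 0.30 SD.

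**The case against.** **Impact is limited.** The Stage 2 primary outcome is validity and reliability, which this gap does not touch. The secondary outcome is symptom frequency, not new-onset frequency, so a total is correct as labelled. Both points stand. They do not rescue the null hypothesis, which concerns what surgery changes.

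**Misattribution is not certain.** A reader might infer that prior sexual problems will be ascribed to technique or hormones. The documents do not support that. It requires prior problems to differ between groups, and nothing in the plan says that they do. The supported statement is that it can happen and could not be detected.

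**Bowel.** A reader might extend the point equally to bowel symptoms, since a primary outcome is "Characterization of genital, urologic, bowel, and sexual symptoms following male-to-female gender confirmation surgery". That is the Stage 1 outcome, analysed by thematic coding, and the Stage 2 null hypothesis does not name bowel symptoms. With intestinal problems over 6 weeks excluded, only shorter episodes escape.

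**Adjustment can do harm.** If hormonal therapy caused the prior complaints, they lie on the path from hormones to later symptoms, and adjusting for them removes part of the hormone effect. This stands and shapes the fix. The hormone aim under Specific aims also does not name sexual symptoms, although the secondary outcome and the regression set no such limit.

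**Different anatomy.** Background/significance describes creation of a neovagina and neoclitoris. Symptoms specific to these cannot predate surgery, so the inflation applies only to complaints that can exist both before and after. This stands and weakens any assumed correlation.

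**Precision.** A reader might expect a narrower standard error from adjustment. The usual factor √(1 − ρ²) belongs to a continuous baseline score in balanced groups. A yes/no history, partly recalled, does not justify claiming it.

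**Open wording.** The pelvic pathology exclusion is not a closed list, and the new questionnaire is not yet written. Either might come to cover prior sexual function, but neither does so as stated.

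**Conclusion.** The point holds for the sexual domain of Stage 2. As written, the plan cannot separate sexual problems that predate surgery from new ones. Those that persist will be counted in postoperative frequency, and the technique comparison can be biased if prior problems differ between groups.

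The size is unknown. The illustrated 36% to 68% share of pre-existing cases, the false differences of 8 to 16 points, and the bias of 0.15 to 0.30 SD rest entirely on assumed rates, full persistence, equal group sizes and assumed imbalance. They show what is possible, not what is expected.

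The consequence falls on the Stage 2 null hypothesis and the secondary outcomes. This is an inexpensive improvement to those analyses and no threat to the questionnaire validation.

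**What to change.** Under Data collection parameters, add *history of preoperative sexual complaints* beside the urologic item. Complete it at enrolment, before surgery where possible and by recall otherwise, and note which applies.

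In the analysis section:

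- include this history as a covariate in the technique regression for sexual symptoms;
- show the hormone association with sexual symptoms both with and without it, and say that prior complaints may lie on the hormone pathway;
- report sexual symptom frequency with and without women who had prior complaints, marking symptoms that have no preoperative counterpart.

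A matching bowel item is optional, given the existing exclusion.

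The cost is one form item, one covariate and one extra tabulation. The drawback is recall over at most 4 weeks for women enrolled after surgery. The plan does not say how many that will be.
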